8.4.6. Adherence and Retention Analyses

The number and percentage of subjects who withdraw from the study, with primary reason, will be summarized by treatment group.

8.4.7. Baseline Descriptive Statistics

Medical history, physical examination, demographics, and baseline characteristics will be summarized and presented by treatment group and overall. Medical history will be presented by MedDRA SOC and PT, summarizing the proportion of subjects who have a condition noted.

Results from the baseline physical examination will be summarized by body system as recorded in the eCRF.

8.4.8. Interim Analyses

There are no interim analyses planned for this study.

8.4.9. Additional Subgroup Analyses

Subgroup analysis (e.g., age, geography, FRAX (if applicable), prior fracture, and baseline BMD, s-PINP, testosterone, and estradiol levels) may be performed and will be described in the SAP.

8.4.10. Multiple Comparison/Multiplicity

As stated in Section 8.4.3, a fixed-sequence testing approach will be employed to control the Type 1 error rate at the 2-sided significance level of 1% for testing the primary and secondary efficacy endpoints. No other adjustments for multiple comparisons will be made.

8.4.11. Tabulation of Individual Response Data

Individual efficacy, PK, and safety data will be tabulated as appropriate.

8.4.12. Exploratory Analyses

Prespecified exploratory variables and analyses are described in Section 8.4.3.

8.5. Sample Size Calculation

A study sample size of 225 subjects (150 in the abaloparatide-SC group and 75 in the placebo group) will provide at least 99% power to detect a mean difference of 6.5% in the percentage change from baseline in lumbar spine BMD at 12 months between the abaloparatide-SC and the placebo groups at a 2-sided alpha level of 0.01, assuming a SD of 6.0% and a drop-out rate of 10%. For the key secondary endpoints, this total sample size of 225 subjects will have 96% power to detect a 2.2% mean difference (SD = 3.5%) of percent change in total hip BMD at 12 months, and 80% power to detect a 2.0% mean difference (SD = 4.1%) of percent change in femoral neck BMD at 12 months.

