During the Treatment Period, subjects will self-administer a single subcutaneous dose of the randomly assigned study medication once a day. Subjects will have clinic visits for study-related protocol procedures at Day 1, Month 1, Month 3, Month 6, Month 9, and Month 12. Study procedures will include the measurement of BMD by DXA and collection of serum samples to assess markers of bone turnover. At each visit, clinical fractures will also be assessed. Serum samples for evaluation of calcium after study drug administration and immunogenicity testing will be drawn at specified visits during the Treatment Period.

Statistical Considerations

The primary population for efficacy analyses will be the Intention-to-Treat (ITT) Population, defined as all subjects randomized into this study. The primary population for safety analyses will be the Safety Population, defined as all subjects who received at least one dose of study medication. The Per-Protocol Population will include all ITT subjects who did not have any significant protocol deviations and will be used for supportive analyses.

Sample Size

A study sample size of 225 subjects (150 in the abaloparatide-SC group and 75 in the placebo group) will provide at least 99% power to detect a mean difference of 6.5% in the percentage change from baseline in lumbar spine BMD at 12 months between the abaloparatide-SC and the placebo groups at a 2-sided alpha of 0.01, assuming a standard deviation (SD) of 6.0% and a drop-out rate of 10%.

For the key secondary endpoints, this total sample size of 225 subjects will have 96% power to detect a 2.2% mean difference (SD = 3.5%) of percent change in total hip BMD at 12 months

and 80% power to detect a 2.0% mean difference (SD = 4.1%) of percent change in femoral neck BMD at 12 months.

Baseline Comparisons

Baseline characteristics, medical history, physical examination, vital signs, and ECGs will be summarized using standard descriptive statistics by treatment group.

Efficacy Analysis

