4.3.2. Handling of Participant Withdrawals or Terminations

If a subject is withdrawn or discontinued from the study, the reason for withdrawal from the study is to be recorded in the source documents and on the CRF. All subjects withdrawn prior to completing the study should be encouraged to complete study procedures scheduled for the Month 12/Early Termination visit as soon as possible, and to return in 1 month for a Follow-up Visit. All AEs should be followed as described in Section 7. Subjects who discontinue or are withdrawn from the study will not be replaced.

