8.4.2. Analysis of the Primary Efficacy Endpoint(s)

The primary efficacy endpoint will be the percent change in lumbar spine BMD from baseline to 12 months. The analyses will be based on the ITT Population.

The missing data from this study will be reviewed carefully to evaluate any missing data patterns. As this study was not designed to systematically collect data from subjects who discontinue treatment early, the "retrieved dropouts" approach for handling missing data is not applicable for this study. To appropriately address the possibility of data missing not at random, the primary analysis will be based on a pattern-mixture model (PMM) analysis with multiple

imputation using the wash-out imputation method. This method uses sequential regression and wash-out imputation methodology to impute missing values after a subject's discontinuation from the study. The missing primary endpoint values for subjects in the abaloparatide-SC group will be imputed with the observed baseline and data from the placebo group; no intermediate values from the abaloparatide-SC group will be used in the imputation for the abaloparatide-SC group. For subjects in the placebo group, intermediate observed values from the completers in the placebo group will be used while imputing missing values during the 12-month Treatment Period. The PROC MI methodology for imputation of monotone missing data patterns will be used to impute the outcome variables at consecutive visits in a sequential (chain) manner. Each of these imputed datasets will be analyzed using analysis of covariance (ANCOVA) with treatment and DXA instrument manufacturer as fixed effects and the baseline lumbar spine BMD as a covariate. Results from all imputed datasets will be combined using PROC MIANALYZE for overall statistical inference. The statistical tests will be 2-sided comparing abaloparatide-SC to placebo; 99% CIs will be presented together with the estimated p-values.

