#### **3** GENERAL STATISTICAL METHODS

### 3.1 Sample Size Planned and Specified in the Protocol

A study sample size of 225 subjects (150 in the abaloparatide-SC group and 75 in the placebo group) will provide at least 99% power to detect a mean difference of 6.5% in the percentage change from baseline in lumbar spine BMD at 12 months between the abaloparatide-SC and the placebo groups at a two-sided alpha level of 0.01, assuming a standard deviation (SD) of 6.0% and a drop-out rate of 10%. For the key secondary endpoints, a total sample size of 225 subjects will have 96% power to detect a 2.2% mean difference (SD=3.5%) of percent change in total hip BMD at 12 months, and 80% power to detect a 2.0% mean difference (SD=4.1%) of percent change in femoral neck BMD at 12 months.

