- 1. Intermittent missing data in the placebo treatment group will be imputed using MCMC methods, assuming MAR. SAS PROC MI will be utilized for this step using the MCMC impute=monotone option. A total of 100 datasets will be created. These datasets will be utilized in Step #2.
- 2. The remaining missing values in the placebo group with a monotone missing data pattern will be imputed in this step. Missing data will be imputed assuming data are MAR. Only data (both observed and imputed) from subjects in the placebo group will be utilized in this step. SAS PROC MI will be used to impute missing values utilizing the monotone reg option. This will be performed for the 100 datasets. After this step, the 100 datasets will be fully imputed for the placebo treatment group.
- 3. The missing values at Month 12 in the abaloparatide-SC group will be imputed in this step. Control-based PMM imputation will be performed. With this imputation model, the missing values in the abaloparatide-SC group will not be constructed from the observed data in the abaloparatide-SC group but rather from the observed baseline and data (including imputed values) from the placebo group at Month 12. The MNAR statement in SAS PROC MI will be used to impute missing values. This will be performed for the 100 datasets.
- 4. A total of 100 fully imputed datasets will be created for both treatment groups. Since multiple imputation is a stochastic method, slight differences in output can be expected for different initial states of the random number generator. The seed numbers will be identified in the SAS programs to allow for reproducibility.

- 5. After the missing data imputation is completed using the above steps, percentage change values will be calculated in each of the imputed datasets at each visit.
- 6. These 100 datasets will be analyzed using ANCOVA models with fixed effect of treatment group and DXA instrument manufacturer, and baseline lumbar spine BMD as a covariate for the primary efficacy endpoint.
- 7. Treatment effects (difference in LS means between treatments) from these 100 analyses will then be combined using Rubin's Method via SAS PROC MIANALYZE procedure for the primary endpoint.

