## Analyses of Key Secondary Efficacy Endpoints:

The primary population for the analysis of the key secondary efficacy endpoints will be the ITT population. The analyses will be performed using PMM analysis with wash-out imputation similar to the analysis model for the primary efficacy endpoint, with the appropriate baseline covariate.

Analyses of the primary and key secondary efficacy endpoints will follow a fixed-sequence testing approach to control the overall Type 1 error rate at the 2-sided significance level of 1%, as described in Section 3.7.

Sensitivity analyses using a MMRM model, sensitivity analyses for addressing the effect of the COVID-19 pandemic, and supportive analyses using LOCF method, as with the primary efficacy endpoint, will also be conducted. For the estimated treatment effects of the key secondary endpoints, 99% CIs will be presented together with the estimated p-values.

The analyses of each of the key secondary efficacy endpoints using the PMM method with washout imputation, the MMRM model, and the ANCOVA model using LOCF method will be repeated using the PP population to support the findings from the ITT population.

Subgroup analyses using PMM analysis with wash-out imputation will be performed on the key secondary efficacy endpoints using the ITT population for each of the subgroups defined in Section 3.8. The analyses will use analysis models as described above using the subset of ITT subjects belonging to the specific subgroup. A forest plot of the estimated least square (LS) mean

differences between the treatment groups (and corresponding 99% CIs) will be presented by subgroup for each of the key secondary efficacy endpoints.

The efficacy analysis using MMRM model for the key secondary endpoints will also be repeated for the Antibody population, in which the subjects who are ADA+ at any post-baseline time point will be compared with subjects who are ADA- at all post-baseline time points.

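### The stated 80% power for femoral neck BMD leaves out the plan's own 10% drop-out; with it, power is about 75%

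*Protocol*

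**What the plan says.** Protocol 8.5 plans 225 men, 150 on abaloparatide-SC and 75 on placebo. For lumbar spine it claims at least 99% power for a 6.5% difference at 2-sided alpha 0.01, "assuming a SD of 6.0% and a drop-out rate of 10" per cent. The next sentence turns to the key secondary endpoints and attributes two powers to the same total of 225: 96% for a 2.2% difference in total hip BMD (SD 3.5%), and "80% power to detect a 2.0% mean difference (SD = 4.1%) of percent change in femoral neck BMD at 12 months". The Protocol synopsis repeats this ("80% power to detect a 2.0% mean difference (SD = 4.1%) of percent change in femoral neck"), and so does SAP 3.1 ("80% power to detect a 2.0% mean difference (SD=4.1%) of percent change in femoral neck BMD at 12 months"). No drop-out rate is attached to the key-secondary sentence, and neither document says that those powers assume complete follow-up.

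Femoral neck is the third and last test in the fixed sequence, at the 2-sided 1% level (Protocol 8.4.3, SAP 3.7). Men who drop out are not replaced (Protocol 4.3.2, SAP 3.10). For the analysis of the key secondary endpoints, SAP 4.3.2 says: "The analyses will be performed using PMM analysis with wash-out imputation similar to the analysis model for the primary efficacy endpoint". Under step 3 of that method in SAP 4.3.1, "the missing values in the abaloparatide-SC group will not be constructed from the observed data in the abaloparatide-SC group"; they are built from placebo data instead.

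**The concern.** All three BMD endpoints are measured by DXA in the same men at the same visits, so Month 12 losses should be broadly alike across sites. A drop-out rate assumed for the spine therefore applies equally to the hip and femoral neck. A reader of the paragraph will take 80% as holding under its planning assumptions.

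The gap is immaterial for lumbar spine, which has power to spare, but not for femoral neck, which has the least margin of the three. Anyone interpreting a non-significant femoral-neck result would rely on this number to judge how likely a true 2.0% difference was to be missed.

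**Working it through.** **Inputs.** Allocation 150:75, 2-sided alpha 0.01, 10% drop-out, femoral neck difference 2.0% with SD 4.1%, total hip 2.2% with SD 3.5%, lumbar spine 6.5% with SD 6.0% (all Protocol 8.5). The 1% level for the key secondaries is confirmed in Protocol 8.4.3.

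**Formula.** Two-sample t-test: standard error SE = SD × √(1/n₁ + 1/n₂), noncentrality δ = difference / SE, df = n₁ + n₂ − 2. Power is the probability that a noncentral t variable with parameter δ exceeds the 0.995 quantile of t on df (the opposite tail is negligible).

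**Step 1: reproduce the stated figure (150 and 75 evaluable).** SE = 4.1 × √(1/150 + 1/75) = 0.580; δ = 2.0/0.580 = 3.449; critical value 2.598 on 223 df. Power = **80.2%** (80.9% by normal approximation). The stated 80% is reproduced with no drop-out.

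**Step 2: apply 10% drop-out.** 150 × 0.9 = 135; 75 × 0.9 = 67.5, so 67 or 68.
- 135 and 68: SE = 0.610, δ = 3.280, critical value 2.600 on 201 df, power = **75.1%**.
- 135 and 67: SE = 0.613, δ = 3.264, critical value 2.601 on 200 df, power = **74.6%**.

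**Step 3: the three endpoints together.**

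| Endpoint | Stated | 150/75 | 135/68 | 135/67 |
|---|---|---|---|---|
| Lumbar spine | at least 99% | >99.9% | >99.9% | >99.9% |
| Total hip | 96% | 96.7% | 94.7% | 94.5% |
| Femoral neck | 80% | 80.2% | 75.1% | 74.6% |

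**Step 4: what 80% would need at 135 and 67.** Either a true difference of 2.11% instead of 2.0%, or an SD of 3.88% instead of 4.1%.

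**Step 5: the planned analysis.** Imputation keeps every randomised man in the model but adds no information about those who left, and building missing active-arm values from placebo data pulls the estimated difference toward zero. As a rough bound, if 10% of active-arm men contribute no effect, the difference becomes 2.0 × 0.9 = 1.8%; with all 225 analysed and SD 4.1%, power is 69%.

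A simulation of placebo-based multiple imputation (10,000 trials, 100 imputations, Rubin's rules, 150/75 randomised) gives the results below. It assumes equal, uninformative drop-out and treats the stated SDs (4.1% femoral neck, 3.5% total hip) as residual SDs. Monte Carlo error is about 0.5 points or less.

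| Missing at Month 12 (active/placebo) | Meaning of the planned difference | Femoral neck | Total hip |
|---|---|---|---|
| 15/8 (all drop-outs) | effect on drug | 64.1% | 90.9% |
| 8/4 (about half) | effect on drug | 72.0% | 94.0% |
| 15/8 (all drop-outs) | effect in all randomised | 76.0% | 96.0% |

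None of the femoral-neck cases reaches 80%.

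**The case against.** **No arithmetic error.** The 10% sits in the lumbar-spine sentence, and the key-secondary sentence names its own base, 225. On that reading 80% is correctly calculated. This stands as far as it goes: the formula is right. But the secondary powers then rest on an undisclosed zero-drop-out assumption, one sentence after 10% drop-out was assumed for the same men.

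**Drop-out is not the same as a missing Month 12 value.** Withdrawn men "should be encouraged to complete study procedures scheduled for the Month 12/Early Termination visit", which includes DXA (Protocol 6.2.13), and SAP 3.12 Table 4 assigns any BMD scan from day 271 onward to Month 12. A man who leaves after about nine months and is then scanned has an observed value. That is a fair point: 135/67 is the limit in which every drop-out lacks one. The number scanned cannot be predicted, since Protocol 8.4.2 says "this study was not designed to systematically collect data from subjects who discontinue treatment early". Even if only 5% lack a value, the t-test gives 77.6%.

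**About 75% is a completers' t-test, not the planned analysis.** True, and the wash-out results depend on points the documents leave open. They do not bring the figure back to 80%.

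**Covariate adjustment may recover precision.** If 4.1% is a raw SD, a covariate correlation of about 0.32 would restore 80% at 135/67. The documents give no correlation, so this cannot be credited.

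**Needing all 225 is slightly strict.** With 222 evaluable men, power is 79.5% by t and 80% by normal approximation. A loss of about 1% is tolerable; 10% is not.

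**The 25% miss chance ignores the testing sequence.** Correct. Femoral neck also needs lumbar spine and total hip to pass. Requiring total hip to pass, the miss chance at 135/67 is about 25–28% for endpoint correlations from 0.9 down to 0, so gatekeeping can only worsen the figure.

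**Conclusion.** The concern holds. The 80% is right for 225 evaluable men and contains no allowance for the 10% drop-out assumed in the same paragraph. With that allowance, femoral-neck power is 74.6–75.1%, about 5 points lower. Total hip is 94.5–94.7% against a stated 96%, a small change.

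These figures rest on the plan's own difference, SD and alpha, a two-sample t-test, and every drop-out lacking a Month 12 value; they are marginal powers, before gatekeeping. The 64–76% range for the wash-out analysis rests on further assumptions that the documents neither confirm nor rule out, so it should be read as conditional.

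The consequence is limited to how a planning figure is reported and later used. The primary endpoint keeps more than 99% power, and Type I error control is unaffected.

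**What to change.** Amend one sentence in Protocol 8.5, the Protocol synopsis and SAP 3.1, in one of two ways:

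- state the key-secondary powers under the 10% drop-out already assumed: about 95% for total hip and about 75% for femoral neck; or
- keep 96% and 80% and say explicitly that they assume no drop-out.

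If a figure for the wash-out analysis is added, give it as a conditional range (about 64–76% for femoral neck, 91–96% for total hip). State with it how many men are assumed to lack a Month 12 scan, whether the planned differences are on-drug or all-randomised, and whether the SDs are residual or raw.

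The cost is a sentence in three places and, under the first option, a femoral-neck figure about 5 points less favourable. Keeping 80% at 10% drop-out would take about 250 randomised men (225/0.9), but the point does not require enlarging the trial.

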8.6. Measures to Minimize Bias

Not applicable.

8.7. Enrollment/Randomization/Masking Procedures

Abaloparatide-SC and placebo study medications will be prepared in a blinded fashion. Data will be reviewed in a blinded fashion and the analysis populations defined prior to database lock and unblinding.

9. ADMINISTRATIVE REQUIREMENTS

9.1. Ethical Considerations

This clinical study will be conducted in accordance with the current version of the ICH Harmonized Guideline for Good Clinical Practice (GCP), with applicable local laws and regulations, and with the ethical principles laid down in the Declaration of Helsinki.

The Investigator will ensure that this study is conducted in full conformity with ICH GCP E6(R2).

The IRB/IEC will review all appropriate study documentation to safeguard the rights, safety, and well-being of the subjects. The study will only be conducted at sites where IRB/IEC approval has been obtained. The protocol, IB, ICF, advertisements (if applicable), written information given to the subjects, safety updates, annual progress reports, and any revisions to these documents will be provided to the IRB/IEC by the Investigator or RADIUS or designee, as allowable by local applicable laws and regulations.

9.2. Subject Information and Informed Consent

The Investigator is responsible for obtaining written, informed consent from each subject interested in participating in this study before conducting any study-related procedures.

Written informed consent should be obtained after adequate, thorough, and clear explanation of the study objectives, procedures, as well as the potential hazards of the study. The method of obtaining and documenting the informed consent and the contents of the consent will comply with ICH GCP and all applicable laws and regulations and will be subject to approval by RADIUS or its designee.

9.3. Investigator Compliance

No modifications to the protocol should be made without the approval of both the Investigator and RADIUS. Changes that significantly affect the safety of the subjects, the scope of the investigation, or the scientific quality of the study (i.e., efficacy assessments) will require IRB/IEC notification before implementation, except where the modification is necessary to eliminate an apparent immediate hazard to human subjects. RADIUS will submit all protocol modifications to the required regulatory authorities.

When circumstances require an immediate departure from procedures set forth in the protocol, the Investigator will contact RADIUS to discuss the planned course of action. If possible, contact should be made before the implementation of any changes. Any departures from protocol must be fully documented in the source documentation.

9.4. Access to Records

The Investigator must make the office and/or hospital records of subjects enrolled in this study available for review by site monitors at the time of each monitoring visit, audit by RADIUS Quality Assurance (QA) and inspection by the regulatory agencies. The records must also be available for inspection, verification, and copying, as required by applicable laws and regulations, by officials of the regulatory health authorities (FDA and others). The Investigator

must comply with applicable privacy and security laws for use and disclosure of information related to the research set forth in this protocol.

9.5. Subject and Data Confidentiality

To maintain subject confidentiality, all eCRFs, study reports and communications relating to the study will identify subjects by assigned subject numbers. As required by federal regulations, the Investigator will allow RADIUS and/or its representatives access to all pertinent medical records to allow for the verification of data gathered in the eCRFs/SAE Forms and the review of the data collection process. The FDA (or other regulatory authority) may also request access to all study records, including source documentation, for inspection.

As applicable, in accordance with the Health Insurance Portability and Accountability Act (HIPAA) and associated privacy regulations, a subject authorization to use personally identifiable health information may be required from each subject before research activities begin.

Subject confidentiality is strictly held in trust by the participating Investigators, their staff, and RADIUS and their representatives. This confidentiality is extended to cover testing of biological samples and genetic tests in addition to the clinical information relating to participants. Therefore, the study protocol, documentation, data, and all other information generated will be held in strict confidence. No information concerning the study or the data will be released to any unauthorized third party without prior written approval of RADIUS.

